7.0 Risks and Discomforts

Protection of Human Subjects

1. The data to be collected from each subject include: medical history and physical examination; sleep EEG and respiration; actigraphy; and self-reported questionnaires and scales.
2. The venous puncture is associated with minor discomfort and a risk of a bruise at the site of the venous puncture.

3. Potential risks include the risk of study-related procedures. There is a minimal risk associated with the discomfort of having standard clinical EEG past electrodes applied to the scalp. Rarely, we have had an individual who has had a mild allergic reaction to the tape applied over electrodes. This risk is minimized by using hypoallergenic tape.

4. There are a few potential risks associated with trazodone. Trazodone is a sedative triazolopyridine antidepressant, habitually used for the treatment of depression and insomnia because it possesses antidepressant and also anxiolytic and hypnotic activities (Al-Yassiri et al, 1981; McCall, 2010). Pharmacologically, it is a serotonin antagonist and reuptake inhibitor; it is a blocker of postsynaptic serotonin receptors 5-HT_{1A}, 5-HT_{1C}, and 5-HT₂, as well as postsynaptic α ₁-adrenergic receptors. It has a peak serum concentration of 1-2 hours and an elimination half-life of about 5-9 hours. When prescribed as an antidepressant, i.e., to alleviate major depression, the usual doses of trazodone are \geq 150 mg daily. Daytime doses of trazodone at 100 mg have been found to impair critical flicker fusion and choice reaction time 1-4 hours later in only two studies (Burns et al, 1986; Warrington et al, 1984). Bedtime doses of trazodone at 100 mg have been found to lower blood pressure and impair critical flicker fusion the next morning in one study (Saletu-Zyhlarz et al, 2001). One study mentioned in a recent review found orthostatic hypotension and priapism as a side effect of bedtime trazodone administration (James and Mendelson, 2004). When prescribed as a hypnotic, it is habitually used at low-doses (i.e., 50 mg daily at bedtime). The vast majority of studies have shown that trazodone improves subjective sleep quality and increases objective total sleep time, percent of stages 3 and 4, and sleep efficiency, and decreases the percent of stage 1, number of awakenings, and stage shifts, as assessed by PSG (Burns et al, 1986; Saletu-Zyhlarz et al, 2001; James and Mendelson, 2004; Dording et al, 2002; Nierenberg et al, 1994; Haffmans, 1999; Walsh et al, 1998; Montgomery et al, 1983; Yamadera et al, 1998; Ware and Pittard, 1990; Kaynak et al, 2004; Zavesicka et al, 2008). There are no controlled studies or clinical reports of major side-effects with low-dose trazodone when administered at bedtime in insomniacs. The most common side effect of low-dose trazodone when administered at bedtime may be minimal morning sedation, based on clinical experience. Common risks of trazodone given at higher doses include headache, dry mouth, blurred vision, dizziness, fatigue, nausea and suicidal thoughts in children, adolescents and young adults with depression.

5. There are a few potential risks associated with CBT. When individuals start the sleep scheduling component they are asked to restrict their time in bed and in some instances their sleep duration. This procedure may cause some residual daytime sleepiness that might interfere with daytime functioning. The patient will be warned of this possible effect and will be asked not to get into risky behaviors if feeling excessively sleepy (e.g., driving). Another possible side-effect of CBT may be the frustration felt by the patient due to a lack of achievement of expected goals. CBT is a goal-oriented, homework-based psychotherapy and in some cases the patient may be delayed to respect to the planned objectives which may cause some frustration. However, we do not anticipate any major side-effects to occur.

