2.0 Objectives

Little is known about the pathophysiology of chronic insomnia whereas the currently available treatments are either partially effective and/or associated with poor outcome in objective measures of nighttime sleep.

Accumulating evidence points to the possibility that chronic insomnia is a state of physiological and emotional hyperarousal. In individuals with chronic insomnia, objective short sleep duration is associated with hyperactivity of the stress system (e.g., hypercortisolemia) and with increased risk of significant medical sequelae, such as cardiometabolic and neurocognitive disorders. It appears that objective measures of sleep may be a reliable index of the biological severity of the disorder. Finally, CBT, the current recommended first-line treatment for chronic insomnia is associated with improvement of subjective sleep quality whereas it does not appear to significantly

improve objective sleep duration. Interestingly, most studies examining the efficacy and/or effectiveness of CBT have been conducted in chronic insomniacs with a rather “normal” (> 6 hours) sleep duration.

Sedative antidepressants, such as trazodone, are widely used by the practicing physician to treat chronic insomnia. However, there is a lack of studies that have examined their efficacy, tolerance, and side effects. Several studies have reported that sedative antidepressants may reduce cortisol levels and/or increase objective sleep duration in chronic insomniacs. As yet, there have not been controlled studies to examine the effects of trazodone versus CBT on severe chronic insomnia, i.e., those with objective short sleep duration.

The primary hypothesis to be tested is that trazodone improves both subjectively and objectively chronic insomnia with objective short sleep duration. Specifically, in this study, we will assess the following specific aim/hypothesis: to examine the effects of trazodone vs. CBT in chronic insomniacs with objective short sleep duration. Specifically, we hypothesize that trazodone will be more effective than CBT in improving both subjectively and objectively chronic insomnia. To test this hypothesis, we propose a pilot, 3-month randomized trial of trazodone compared to CBT in 24 male and female patients with chronic insomnia with objective short sleep duration.

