
Table 4. A session-by-session schedule of the CBT program

Session	New/Review*	Content	Duration
1	N	Conceptual model and sleep hygiene	50 min
2	N	Setting up sleep restriction and stimulus control, Set prescription for sleep restriction	50 min
3	R	Sleep restriction and stimulus control treatment gains and compliance	50 min
4	R	Sleep restriction and stimulus control treatment gains and compliance	50 min
5	N	Cognitive therapy	50 min
6	R	Cognitive therapy	50 min
7	R	Cognitive therapy, sleep restriction, and stimulus control gains and compliance	50 min
8	N	Discuss relapse prevention Post-treatment assessment	50 min

* New/Review refers to the introduction of a new clinical component vs. a review of the outcomes and adherence of previously introduced components.

This **CBT protocol** is designed to be implemented over a period of 12 weeks, with consultation sessions held on a weekly basis (Perlis et al, 2005). There will be 2 sessions devoted to baseline evaluation, along with a 2-week baseline sleep diary and actigraphy monitoring period, followed by 8 therapy sessions. This number of sessions is needed to present a conceptual behavioral model of insomnia, describe all clinical procedures and their rationale, provide enough time for patients to experiment with those procedures at home, and to problem-solve difficulties encountered during home practice. Clinical sessions will be held weekly, to ensure continuity between sessions. The treatment program described here has been validated according to specific parameters (Perlis et al, 2005). Individual therapy sessions will last approximately for 50 minutes. Each therapy session is highly structured and covers a different aspect of treatment. Although their specific content varies on the technique presented/used, most sessions are structured according to the agenda outlined in Table 5.

Table 5. CBT session agenda

-
- Review sleep diary.
 - Evaluate compliance with clinical procedures and homework assignment.
 - Identify problems during home practice and strategies for promoting treatment adherence.
 - Introduce new treatment component and its rationale.
 - Present didactic material supporting this component.
 - Review homework assignments for the upcoming week.
-

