The very first item of the agenda is to review the sleep diary for the previous week. This provides a clear message to the patient that self-monitoring is expected and is an essential component of therapy. The next step is to check the extent to which the patient has complied with previous recommendations. After problem solving adherence issues, a new treatment component is introduced. Each procedure is described along with its rationale and objectives. Handouts will always be provided to consolidate the new information presented during the session. The final item on the agenda is to review homework assignment for the upcoming week giving a written summary to the patient.

The **trazodone group** will receive a standard handout on sleep hygiene instructions and subsequent biweekly and monthly visits to check treatment effectiveness, adherence and possible side-effects, if they occur, and also follow-up review of sleep hygiene practices. All patients will receive a standard dose of trazodone 50 mg. in their first visit and will be followed-up with 2 additional biweekly visits. During these biweekly visits, doses will be adjusted according to drug effectiveness and possible side-effects. Consecutive visits will be scheduled monthly and will focus on assessing treatment effectiveness, adherence and possible side-effects and need to adjust medication doses.

Techniques

1. Medical History and Physical Examination

Each subject will have a complete medical history and physical examination using a semi-structured format and a battery of clinical tests, including complete blood count, liver function test, urinalysis, lipid panel, thyroid indexes, and electrocardiography. Pre-menopausal women will also have a pregnancy test performed. Blood pressure will be measured in the morning and in the evening using a pneumoelectric microprocessor-controlled instrument. The recorded blood pressure will be the average of 3 consecutive readings during a 5-minute period following 10 minutes of rest in the supine position. Anthropometric measures will include height, weight, neck size, and waist and hip measurements according to standard procedures. Specifically, neck size is measured at the superior border of the cricothyroid membrane with the subject in the upright position. Waist is measured at or 1 cm above the umbilical midline and hip at the widest area around the buttocks.

2. Objective assessment of Nighttime Sleep

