e. Pre-sleep Arousal – The Pre-Sleep Arousal Scale (PSAS) will be used for assessment of the subjects' perceived pre-sleep cognitive and somatic arousal at the onset of the study, at the end of the intervention and at follow-up (Nicassio et al, 1985).

f. Arousability – The Arousability Predisposition Scale (APS) will be used for assessment of the subjects' perceived overall tendency to present high levels of cognitive and emotional arousal at the onset of the study, at the end of the intervention and at follow-up (Coren, 1988).

g. Stress-related Insomnia – The Ford Insomnia Response to Stress Test (FIRST) will be used for assessment of the subjects' overall perceived likelihood of having sleep disturbances in association with specific and common stressful events at the onset of the study, at the end of the intervention and at follow-up (Drake et al, 2004).

4. Assessment of Daytime Functioning

a. Sleepiness and Fatigue – Subjects will estimate degree of sleepiness/alertness after awakening in the sleep lab with a 10-cm analog scale that ranges from "extremely sleepy" to "not sleepy" and the Stanford Sleepiness Scale (SSS) (MacLean et al, 1992). The Epworth Sleepiness Scale (ESS) will be used for assessment of the subjects' overall sleepiness at the onset of the study, at the end of the intervention and at follow-up (Johns, 1991). The Fatigue subscale of the Profile of Mood States (POMS-F) (McNair et al, 1971.), and the Multidimensional Fatigue Inventory (MFI) (Smets et al, 1995) will be used for assessments of the subjects' overall fatigue at the onset of the study, at the end of the intervention and at follow-up.

b. Mood – The Beck Depression Inventory-II (BDI-II) will be used for assessment of the subjects' overall severity of depressive symptoms at the onset of the study and at the end of the intervention (Beck et al, 1996). The Beck Anxiety Inventory (BAI) will be used for assessment of the subjects' overall severity of anxious symptoms (somatic component) at the onset of the study, at the end of the intervention and at follow-up (Osman et al 1997). The Anxiety subscale of the Hospital Anxiety and Depression Scale (HAD-S) will be used for assessment of the subjects' overall severity of anxious symptoms (cognitive component) at the onset of the study, at the end of the intervention and at follow-up (Zigmond and Snaith, 1983).

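### A side-effect check is written only into trazodone visits, and neither arm has a sleepiness scale during treatment, so early sleepiness may be under-recorded and adverse-event counts by arm would partly reflect how events were sought

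*Combined protocol and SAP*

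**What the plan says.** **CBT risk.** Section 7.0, item 5, names daytime sleepiness when time in bed is restricted: "This procedure may cause some residual daytime sleepiness that might interfere with daytime functioning". The stated response is advice: "The patient will be warned of this possible effect and will be asked not to get into risky behaviors if feeling excessively sleepy". No measurement is attached to it.

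**CBT schedule.** In Table 4, session 2 is "Setting up sleep restriction and stimulus control, Set prescription for sleep restriction". Sessions 3, 4 and 7 return to restriction. Section 6.0 adds: "Clinical sessions will be held weekly, to ensure continuity between sessions". The Table 5 agenda covers the diary, compliance ("Evaluate compliance with clinical procedures and homework assignment"), problems in home practice, the new component and homework. It has no side-effect item.

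**Trazodone schedule.** Section 6.0 gives this arm "subsequent biweekly and monthly visits to check treatment effectiveness, adherence and possible side-effects, if they occur". Section 7.0, item 4, says that the most common effect of a low bedtime dose may be slight morning sedation.

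**Sleepiness scales.** Section 6.0 uses the ESS for "overall sleepiness at the onset of the study, at the end of the intervention and at follow-up". The Stanford Sleepiness Scale (SSS) and the analog scale are completed on mornings in the sleep laboratory. In Table 3 the treatment-visit columns of both arms hold only the sleep diary and the Insomnia Severity Index (ISI).

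**Adverse events in general.** Sections 9.0 and 13.0 require the principal investigator to document and report all adverse events, and to review them cumulatively every six months. Neither section says how or when patients are to be asked.

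**The concern.** There are two gaps, and they should be kept apart.

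The first differs between the arms. One arm has a written side-effect check and the other does not. If staff follow the plan as written, an event of the same kind has a better chance of being recorded on trazodone. A count by arm then mixes the treatment's effect with the effect of enquiry, and the data collected offer no means of estimating the second.

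The second is the same in both arms. Sleepiness is a named risk of each treatment, yet it is not scored in the weeks when restriction is being applied or the trazodone dose adjusted. Sleepiness that appears early and then settles would leave no trace on the scales at 3 months.

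The records matter because section 13.0 has the principal investigator act on cumulative events that alter the balance of risk and benefit, and section 8.0 expects the data to help design larger trials. Section 2.0 also gives as background for sedative antidepressants that "there is a lack of studies that have examined their efficacy, tolerance, and side effects".

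**Working it through.** The plan states no figure for the interval or for the number of checks. Both are derived here from section 6.0 and Tables 3 to 5.

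**1. Planned side-effect checks before the 3-month evaluation**
- Trazodone: after the first visit, two biweekly visits (about weeks 2 and 4), then monthly (about week 8). Total: about 3.
- CBT: sessions whose written content includes a side-effect check = 0 of 8. Six sessions (3 to 8) follow the session at which restriction is set, so 0 of those 6.

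**2. Weeks from session 2 to the next sleepiness score**

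Interval = week of the assessment − week of session 2. Three months is taken as week 12 or 13.

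| Reading of the schedule | Session 2 at week | Interval (weeks) |
|---|---|---|
| Therapy starts the clock, session 1 at week 0 | 1 | 12 − 1 = 11, or 13 − 1 = 12 |
| Therapy starts the clock, session 2 in week 2 | 2 | 12 − 2 = 10, or 13 − 2 = 11 |
| The two baseline sessions lie inside the 12 weeks | 4 | 12 − 4 = 8, or 13 − 4 = 9 |
| Baseline sessions and the 2-week diary lie inside the 12 weeks | 6 | 12 − 6 = 6, or 13 − 6 = 7 |
| Post-treatment assessment takes place at session 8, sessions weekly | – | 8 − 2 = 6 |

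The range is 6 to 12 weeks. It is this wide because section 6.0 describes a 12-week programme with 8 weekly therapy sessions, an evaluation after 3 months, and a post-treatment assessment at session 8 that refers to Table 3. Even at 6 weeks, sessions 3 to 7 pass without a sleepiness score.

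**3. What unequal enquiry could do (assumed inputs)**

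Take 24 randomised patients as 12 per arm. Assume the same true event rate p in both arms, full capture on trazodone, and a fraction c captured on CBT. Expected records are 12p on trazodone and 12pc on CBT.

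| p | Trazodone | CBT, c = 75% | CBT, c = 50% | CBT, c = 25% |
|---|---|---|---|---|
| 20% | 2.4 | 1.8 | 1.2 | 0.6 |
| 30% | 3.6 | 2.7 | 1.8 | 0.9 |
| 50% | 6.0 | 4.5 | 3.0 | 1.5 |

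At c = 50%, equal risk looks twice as high on trazodone. The documents give neither p nor c, so this shows direction and scale only.

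**4. Precision with equal enquiry**

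With p = 30% in both arms, the 95% half-width for a difference in rates is 1.96 × √(2 × 0.3 × 0.7 / 12) = 1.96 × 0.187 = 0.37, about ±37 percentage points.

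**The case against.** The strongest reply is that the protocol does not leave CBT patients unobserved, and that no planned analysis is harmed. Much of this stands.

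- **Is the risk missed?** A reader might infer so, but the text does not support it. Patients are warned. Sessions 3 and 4 take up difficulties with the techniques, starting about one week after restriction is set; session 7 does so again, and Table 5 looks for problems in home practice. CBT patients also have more contacts than trazodone patients. What remains is that these items concern technique and adherence, so sleepiness may come up but nothing requires it to be asked about or recorded.
- **Does zero of 8 mean that nobody asks?** No. Section 6.0 says that most sessions, not all, follow the Table 5 agenda. The count is of written items, not of practice.
- **Is this prompted against spontaneous reporting?** That goes too far. The trazodone check has no script or form, and the duty to document events covers both arms. Unequal capture is plausible, but its size is unknown.
- **Does the timing of the sleepiness scales favour one arm?** No. The ESS and SSS are scheduled identically in both arms. Their absence during treatment is a shared gap in measurement.
- **Does the trial plan to compare safety between arms?** No. Adverse events are not among the outcomes in section 2.0, section 11.0 has no safety analysis, and section 13.0 describes a cumulative review. The section 2.0 remark on side effects describes the literature; it is not an aim of the trial.
- **Would better capture help in so small a trial?** Only modestly for comparison, given ±37 points. But individual safety detection and the use of the data for later trials do not depend on a formal comparison.

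**Conclusion.** The point holds in a limited form. As written, a side-effect check is planned at about 3 trazodone visits before the 3-month evaluation and at none of the 8 CBT sessions. In both arms, sleepiness is unscored from baseline to the end of treatment, which is about 6 to 12 weeks after CBT restriction is set. Early sleepiness may therefore be under-recorded, and any count of adverse events by arm would partly reflect how events were sought.

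This rests on staff following the written agendas, on weekly CBT sessions, and on the visit timing derived above. The documents do not support a single firm interval such as 10 weeks, nor a claim that the CBT risk goes unmonitored. The bias in counts cannot be sized from the documents. The change is worth making because it is cheap and concerns measurement only.

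**What to change.** 1. **Same question in both arms.** Add one short scripted adverse-event question to Table 5 and to every biweekly and monthly trazodone visit, including drowsy driving, falls and accidents. Use the same form. Fix a common recall period, because CBT visits are weekly and trazodone visits are biweekly and then monthly. The first CBT enquiry after restriction is set would then come at session 3, one week later, and such checks would rise from 0 of 6 to 6 of 6.
2. **Score sleepiness during treatment.** In Table 3, add the ESS at existing visits in matched weeks, for example weeks 4 and 8 (or the nearest session), counted from the first therapy session or the first trazodone visit. Week 2 is too early, because restriction is only being prescribed at about that time.
3. **Report by arm.** Tabulate events by arm in the six-monthly review and label the comparison descriptive.
4. **Reconcile the timing.** State how the 12-week programme, the session 8 assessment and the 3-month evaluation fit together, so that the week 8 ESS and the end-of-treatment ESS are distinct.

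The cost is a protocol amendment, one form and a few minutes per existing visit. More minor events will probably be recorded in the CBT arm, and the report should say that enquiry was made equal by design.

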8.0 Benefits

Risk to Benefit Ratio Only – In our opinion, these studies will provide significant new information in regard to the underlying mechanism of chronic insomnia and will lay the foundation for new treatments for a disorder that affects a large proportion of the general population. In addition, trazodone may hold the benefit of improving sleep duration in chronic insomnia, and a long-term reduction in the risk of developing cardiometabolic and/or psychiatric problems. The benefit to others may be validation of trazodone as the basis for treatment of a common sleep disorder with significant medical sequelae. Data obtained in this study can be used to design larger multi-center trials testing these findings. We believe that overall, the risks of these experiments are small compared to the importance of the knowledge that will be obtained.

9.0 Reporting of Adverse Events and Unanticipated Problems Involving Risks to Participants or Others

The PI will report all adverse events or unanticipated problems to the IRB/HSPO according to established guidelines.

10.0 Study Withdrawal/Discontinuation

Taking part in this research study is voluntary. The participants do not have to participate in this research. If they choose to take part, they have the right to stop at any time. If they decide not to participate or if they decide to stop taking part in the research at a later date, there will be no penalty or loss of benefits to which they are entitled and just need to notify the primary investigator that they wish to discontinue.

The research investigators may also discontinue any participant. Possible reasons for this are: continuing the research would be harmful, they did not follow the instructions of the study doctor, or they experience serious side effects.

